---

## Study Summary

Title	High Velocity Nasal Insufflation (Hi-VNI) Use in Upper Airway Surgery
Short Title	Hi-VNI Use in Upper Airway Surgery
IRB Number	834412
Methodology	Prospective, interventional, pilot study
Study Duration	1 year
Study Center	Single center (University of Pennsylvania)
Objectives	

• To establish the efficacy of Hi-VNI in upper airway surgery from the anesthesiologist's and surgeon's perspectives

• To describe the ideal patient and the ideal pathology as well as suitable clinical scenarios when Hi-VNI should be selected

Number of Subjects	100
Main Inclusion and Exclusion Criteria	
Inclusion criteria: Adult patients who are scheduled to undergo elective upper airway surgery at Penn.
 
Exclusion criteria: All patients with underlying medical conditions in which brief periods of hypoxemia or hypercarbia are not well tolerated will be excluded. Patients in whom delivery of air with oxygen via nasal passages is contraindicated will be excluded.
 

• Coronary artery disease

• Severe heart failure with EF < 40% or implanted ICD

• Pulmonary hypertension or pulmonary fibrosis

• History of increased intracranial pressure

• History of skull base or intracranial surgery

• Severe nasal obstruction

• Extremely low or extremely high BMI (BMI <16 or >40)

• Patients at high risk for aspiration

• Patients taken to OR for urgent or emergent upper airway surgery

Intervention	This study will involve use of Hi-VNI device as a primary or adjunct method for oxygenation.
Statistical Methodology	Mann-Whitney U test or Student's t-test and Kruskal-Wallis or ANOVA test will be used depending on the data distribution and the number of variables.
Data and Safety Monitoring Plan	The PI and sub-Is for this study will be responsible for the safety of the subjects enrolled into this study.

CONFIDENTIAL

This material is the property of the University of Pennsylvania.

## Background and Study Rationale

This study will be conducted in full accordance with all applicable University of Pennsylvania Research Policies and Procedures and all applicable federal and state laws and regulations.

### 1 Introduction

The most challenging aspects of laryngeal and laryngotracheal procedures are difficulty of exposure and airway management. These procedures require use of microlaryngeal instruments through a small lumen of a rigid laryngoscope, and are oftentimes difficult to perform with a standard endotracheal tube in place. Similarly, when performing endoscopic evaluation of the trachea, access to the space and visualization of the entire 360-degree view of the trachea is crucial.

To overcome these challenges, a number of techniques for oxygen delivery have evolved over time. Among them are use of a small endotracheal tube, use of jet ventilation and intermittent apnea with periodic removal of the endotracheal tube. The aforementioned methods of airway management carry inherent risks of airway injury, can be accompanied by brief periods of hypoxia or hypercarbia, and can sometimes lead to tenuous airway management scenarios for both the surgeon and the anesthesiologist when clear communication and familiarity with the airway management plan during the procedure are sub-optimal. For this reason, there is an ongoing search for acceptable solutions to minimize these risks during upper airway surgery.

One of the newly emerging advanced oxygenation techniques, also known as Hi-VNI (High Velocity Nasal Insufflation), allows for delivery of humidified oxygen through a specialized high-flow nasal cannula at rates of up to 40 l/min. This non-invasive high flow respiratory support system is currently being used in the treatment of respiratory failure in both adult and pediatric patients. This technique provides sustained oxygenation due to reduction in airway resistance, a build-up of airway pressure with oxygen-rich gas and active gas exchange, which lead to flushing of anatomic dead space, and delivery of oxygen into the lungs. This oxygenation technique can be used both in spontaneously breathing patients and under apneic conditions, while providing an unobstructed surgical view with the glottis, subglottis and trachea fully accessible for instrumentation.

The goal of this study is to establish the efficacy of Hi-VNI in upper airway surgery, to document the advantages and disadvantages of this technique from the standpoint of the airway surgeon and the anesthesiologist, and to provide more information about the optimal patient and airway pathology as well as suitable clinical scenarios when Hi-VNI device can be used for oxygenation during upper airway surgery. We hypothesize that in appropriate clinical situations, Hi-VNI can ease airway management, shorten case duration, and provide superior operating conditions including space for instrumentation during upper aerodigestive tract procedures.

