## **2.2 Secondary Objectives**

To collect clinical information about the effect of Hi-VNI use on procedure duration with the specific focus on:

- The effect of this technique on the duration of the induction phase of anesthesia, surgical procedure duration, and the duration of emergence from anesthesia
- Ease of use and any intra-operative and post-operative difficulties that may arise from use of this oxygenation technique

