### **3.2 Allocation to Interventional Group**

All subjects included in this study will undergo the same intervention, defined as the use of Hi-VNI as primary or adjunct oxygenation technique.

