#### 3.4.2 Secondary Study Endpoints

The secondary endpoints for the study will be the total case duration (induction to end of surgery), the time from the end of the case to emergence from anesthesia, nadir SpO2, peak TcpCO2, and rate of change in TcpCO2 (transcutaneous CO2).

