## **6 Statistical Plan**

### **6.1 Sample Size and Power Determination**

The subjects will be recruited prospectively based on the eligibility criteria for this study. The investigators anticipate that 100 subjects will be recruited for this study between January 2020 and January 2021. This sample size is determined based on the previously noted caseload for our practice and the fact that this study duration will be limited to one year only. No comparison or control group will be used for this study. The calculation of statistical power will not be required. Patel et al showed that a rate of rise in pCO2 was 0.15 kPa/min with Hi-VNI oxygenation while measuring end tidal CO2 transcutaneously, which translates into 1.125 mmHg/min. Another study by Gustaffson et al cited average apnea duration during elective

laryngeal surgery of  $22.5 \pm 4.5$  min. Based on these values of the rate of rise for pCO2 and the average apnea duration for elective laryngeal surgery, assuming normal data distribution, the range of TcpCO2 change for procedure length within one standard deviation of the mean value (22.5 min) will be [20.25; 30.38].

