## **6.2 Statistical Methods**

Descriptive statistics will be used to characterize the data distribution with normally distributed data presented as means and standard deviation, otherwise median and interquartile range will be used. Proportions will be presented in numbers and percentages. All data analyses will be performed using a statistical tool (SPSS, version 15.0, SPSS). Mann-Whitney U test or Student's t-test and Kruskal-Wallis or ANOVA test will be used depending on the data distribution and the number of variables. All statistical analyses will use a  $p < 0.05$  as statistically significant. Any additional statistical analyses will be determined during secondary data analysis with help from a statistician.

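### The hypothesis that Hi-VNI shortens cases and gives superior conditions cannot be supported by a single-arm study, and section 6.2 leaves open a completed-versus-switched comparison that would be confounded by duration

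*Combined protocol and SAP*

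**What the plan says.** **The question.** The hypothesis in section 1 is that, in suitable situations, Hi-VNI can ease airway management, "shorten case duration, and provide superior operating conditions including space for instrumentation during upper aerodigestive tract procedures". Section 2.2 sets out to collect information on "The effect of this technique on the duration of the induction phase of anesthesia, surgical procedure duration, and the duration of emergence from anesthesia". Section 3.3 adds that video review will help show how a tubeless field affects the length of the case. Section 3.4.2 makes total case duration and time to emergence secondary endpoints.

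**The design.** Section 3.2: "All subjects included in this study will undergo the same intervention". Section 6.1: "No comparison or control group will be used for this study" and "The calculation of statistical power will not be required". Section 1.1 names current practice (jet ventilation or a small endotracheal tube) but gives no duration figure for it. Sections 3.4.1 and 3.4.2 list no measure of operating conditions. Section 3.3 says only that ease of use and any difficulties will be recorded.

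**The analysis.** Section 6.2: "Mann-Whitney U test or Student's t-test and Kruskal-Wallis or ANOVA test will be used depending on the data distribution and the number of variables", with p<0.05 as the criterion. It names neither the groups nor the endpoints to be tested.

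**The concern.** Shorter, superior and effect on duration all need something to be compared with. In this design nothing is available, inside or outside the study. A duration observed under Hi-VNI can be described, but it cannot be called shorter.

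The second difficulty is the unassigned tests in section 6.2. Sections 3.1 and 3.4.1 define one split that separates Hi-VNI alone from other oxygenation: cases completed on Hi-VNI versus cases switched to another mode. Section 6.1 treats reaching the CO2 limit as a matter of how long the procedure lasts and deduces that only the shorter procedures avoid a switch. Comparing durations across that split would partly compare short cases with long ones. The result would lean towards the device and could be published as evidence that Hi-VNI saves time.

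**Working it through.** **1. The plan's own figures.** Section 6.1 takes a duration of 22.5 min (SD 4.5, normal), a CO2 rise of 1.125 mmHg/min and a start of 37.5 mmHg.
- One SD either side of the mean is 18 to 27 min. The rise is 18 × 1.125 = 20.25 to 27 × 1.125 = 30.38, and the end values are 57.75 to 67.88. These match the plan.
- Share below 18 min: Φ(−1) = 15.87% (plan: 15.85%).
- Sample size: 1.96² × 0.16 × 0.84 / 0.05² = 206.5. With a finite population correction for the 144 qualifying cases, 206.5 / (1 + 205.5/144) = 85.1, rounded up to 86; 86 + 14 = 100. This matches the plan.

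The 100 therefore comes from a precision calculation for the completion rate. It does not address a duration comparison.

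**2. The switch as a time rule.** Two cuts follow from section 6.1. Its 16% uses 18 min. Its 55 mmHg threshold implies (55 − 37.5)/1.125 = 15.6 min. The two do not agree (18 min corresponds to 57.75 mmHg) and should be reconciled; both are carried here.

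**3. Mean durations if Hi-VNI has no effect.** With a = (cut − 22.5)/4.5, completed cases average 22.5 − 4.5 φ(a)/Φ(a) and switched cases 22.5 + 4.5 φ(a)/(1 − Φ(a)).
- 18 min, a = −1: 22.5 − 4.5 × 0.2420/0.1587 = 15.6; 22.5 + 4.5 × 0.2420/0.8413 = 23.8. Difference 8.2 min.
- 15.6 min, a = −1.543: 22.5 − 4.5 × 0.1213/0.0614 = 13.6; 22.5 + 4.5 × 0.1213/0.9386 = 23.1. Difference 9.5 min, with 6.1% of cases completed.

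**4. Sensitivity.** Simulated studies of 100 with zero true effect, 4,000 per row, tested two-sided at 0.05. The last column counts significant results that favour completed cases. Tests are t-tests, or Mann-Whitney where marked MW. Studies with fewer than two cases in a group were set aside. Everything beyond the plan's inputs is an assumption.

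| Assumption about switching | Spurious difference (min) | Significant |
|---|---|---|
| Fixed cut at 18 min; at 15.6 min | 8.2; 9.5 | about 100% |
| Rise varies between patients, SD 0.2; 0.4 mmHg/min | 6.4; 3.3 | over 99%; 85% (MW) |
| Same, plus independent induction time, SD 5 min | 6.4; 3.3 | about 87%; 53% (MW) |
| Rise varies, CV 20%; 30%; 50% | 5.9; 4.0; 2.3 | 99%; 95%; 67% |
| Slower mean rise, 0.6 to 0.8 mmHg/min, CV 30 to 50% | 2.8 to 4.7 | 89% to 100% |
| 18-min cut, and 10 to 50% of would-be completers switched for reasons unrelated to time | 8.0 to 7.5 | about 100% |
| Constant switching hazard, with 16%; 50%; 80% still on Hi-VNI at 22.5 min | 2.0; 1.3; 1.0 | 38%; 30%; 14% |
| Switching independent of duration | about 0 | 2.8% |

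The sign favours completed cases in every row where time on Hi-VNI raises the chance of a switch. Time spent on the switch itself is not modelled; it would add to the apparent shortening.

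**The case against.** Section 3.1 calls this a pilot study that will describe cases, section 6.2 opens with descriptive statistics, and the hypothesis is hedged. Three stronger readings are tempting, and the documents do not support them.

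- A reader might infer that section 2.2 itself claims shorter cases or superior conditions. It does not. It asks for information on the effect on durations; the directional words are in section 1.
- A reader might infer that the plan schedules a completed-versus-switched test of duration and so will produce a biased result. No section does. Section 6.2 leaves groups and endpoints unnamed, so the comparison is one it permits.
- A reader might infer that this is the only possible split. Others are conceivable: apneic versus spontaneously breathing (2.1), or primary versus adjunct use (3.2). Completed versus switched is only the split that isolates Hi-VNI alone.

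The objection to the size also stands. The 22.5 ± 4.5 min is a cited apnea duration, while the endpoint in section 3.4.2 runs from induction. Section 3.3 also allows switches for low SpO2, arrhythmia, hypotension, bleeding or laser need. It expects most cases to finish within 20 min, whereas the assumed distribution puts only 29% there. The simulation is therefore an illustration.

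The pilot label does not remove the main point. A pilot may describe durations, but this one states a directional hypothesis, aims to establish efficacy, sets a significance level and intends publication.

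**Conclusion.** The comparative hypothesis is wrong as written for this design. With one arm, no benchmark and no operating-conditions endpoint, the study cannot conclude that cases are shorter or conditions superior, and it cannot estimate the effect on duration that sections 2.2 and 3.3 seek. This follows from the text alone and needs no simulation.

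The conditional part is that a completed-versus-switched comparison of durations would be confounded in favour of Hi-VNI. Its size ranges from about 1 min, under a constant switching hazard, to 9.5 min, under the plan's inputs taken literally. The chance of a significant result ranges from about 14% to nearly 100%. The direction requires only that longer time on Hi-VNI makes a switch more likely. The completion-rate endpoint in section 3.4.1 is not affected.

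**What to change.** 1. Reword the hypothesis in section 1 and the objective in section 2.2 to: *describe induction, procedure and emergence durations and operating conditions with Hi-VNI*. Bring the video-review sentence in section 3.3 into line, and state what will be recorded as operating conditions.
2. In section 6.2, report durations as median (IQR) with a 95% CI, and name the groups and endpoints of any test that is kept.
3. State in section 6.2 that differences in duration between completed and switched cases will not be interpreted or presented as an effect of Hi-VNI. Procedure length may still be described as a predictor of completion, which serves the aim of identifying suitable cases.
4. Draw no conclusion of shorter cases or superior conditions from this study.

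The cost is protocol and analysis-plan wording, and a more modest claim. Keeping the comparative claim would instead need a prespecified concurrent or matched historical group under current practice and a defined rating of operating conditions, which is a larger change.

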## **1.1 Background and Relevant Literature**

Upper airway surgery is performed to treat a number of laryngeal and laryngotracheal conditions, many of which require an unobstructed view of the glottis, the subglottis, and the trachea. Various techniques of airway management have evolved over time to meet these requirements. These techniques include use of a small size endotracheal tube, intermittent apnea (periods with no breathing or oxygenation) during periodic removal of the endotracheal tube, and jet ventilation. The aforementioned methods of airway management allow for completion of the surgical procedures in the airway, but carry inherent risks of airway injury, can be accompanied by periods of hypoxia or hypercarbia, and can sometimes lead to tenuous airway management scenarios.

Traditionally, before endotracheal intubation during surgical procedures, pre-oxygenation with a facemask is combined with apneic oxygenation via nasal cannula at rates of up to 15 mL/min. Apneic oxygenation with nasal cannula prolongs the safe apnea time, defined as the apnea time before desaturation. Recent advances in the field of anesthesia and oxygenation techniques introduced the Hi-VNI (High Velocity Nasal Insufflation) oxygenation technique. Hi-VNI technology has been utilized in cases of spontaneously breathing or apneic patients. Hi-flow nasal oxygen has been advocated to improve safety in bridging oxygenation of high-risk patients during apnea induced for urgent or emergent intubation. Prior studies suggest that it prolongs the safe apnea time in physiologically fragile patients who cannot be ventilated by facemask due to risk of aspiration or challenging airway anatomy.

Our current approach in upper airway surgical procedures employs high-frequency jet ventilation (HFJV) or intubation with a small size endotracheal tube. In upper airway surgery, Hi-VNI oxygenation offers the advantage of an unimpeded and more stationary surgical view, while avoiding the risk of barotrauma when compared to jet “ventilation”, and can deliver oxygenation in severe cases of airway obstruction such as cases of laryngotracheal stenosis when passage of the endotracheal tube or insertion of the jet ventilation cannula is difficult. Hi-VNI may be advantageous as it produces less field motion when compared to HFJV, requires less technical expertise of the operator (requires a simple adjustment to titrate the rate of flow and oxygen content of the delivered humidified gas), does not entail instrumentation of the airway with a HFJV catheter or endotracheal tube, is not associated with the risk of barotrauma sometimes seen with HFJV, and allows for continuous oxygenation (HFJV needs to be paused during certain parts of the procedure to allow for a motionless field).

Most upper airway procedures we perform are short duration procedures and can be completed under apneic conditions or under the conditions of intermittent apnea if the safe apnea time is extended. Multiple recent case reports and small case series described instances where Hi-VNI-type devices extended the safe apnea time and improved patient safety. Wong et al. demonstrated that use of high-flow nasal oxygenation maintained the safe apnea time 40% longer (mean difference of 76 sec) when compared to facemask ventilation in morbidly obese patients (case series of 40 patients). Lee and Quek described a case report of a morbidly obese patient (BMI of 40) undergoing a short laryngeal procedure (pan-endoscopy and vocal cord biopsy) with Hi-VNI providing adequate oxygenation without a need for adjunct methods of oxygenation/ventilation. Hi-VNI has been recommended for use in

critically ill patients during intubation in the ICU to prolong the safe apnea time and to help avoid emergent cricothyrotomy and tracheotomy. Other studies described the benefits of high-flow nasal oxygenation in patients with respiratory distress requiring emergent intubation in the Emergency Department This literature supports the concept that Hi-VNI devices can be used in apneic conditions to maintain adequate oxygenation.

We performed eight short cases of microlaryngeal surgery using Hi-VNI device at our institution, and noted better access to the glottis and the subglottic area with improved oxygenation and delay in desaturation under apneic conditions. These results and current literature on this technique call for further investigation of Hi-VNI use during upper airway surgery to provide additional information to the airway surgeon and the anesthesiologist regarding the most suitable patient and clinical scenario for its use based on the physiologic changes that occur when Hi-VNI is used for oxygenation.

Preliminary investigations published thus far provide some information about the physiologic changes that take place during Hi-VNI oxygenation under apnea. Ebeling et. al. described three cases of laryngeal and laryngotracheal surgery performed using Hi-VNI oxygenation with SpO2 maintained about 97% in all three cases, although their measured rise in pCO2 after 15 minutes of apnea, was slightly higher than previously noted. Other studies documented use of this oxygenation technique with prolonged apnea without desaturation of up to 65 minutes during continuous endoscopic procedures or in pediatric laryngeal surgery. Lyons et al. in their series of 28 patients undergoing laryngotracheal procedures with high-flow nasal oxygenation as a sole oxygenation method showed that only 4 patients had brief desaturations (<2 min) to the levels of SpO2 85-90% supporting use of Hi-VNI during laryngotracheal procedures. None of the studies included here reported adverse events related to Hi-VNI use, and in most instances the authors reported that Hi-VNI device was used as a sole method of oxygenation and provided adequate support. Our study will help address some of the limitations in the currently available knowledge about the use of Hi-VNI in surgical procedures of the upper aerodigestive tract and will contribute to the growing body of literature in this rapidly evolving area. Moreover, this study will help document the advantages and the disadvantages of Hi-VNI use from the standpoint of the upper airway surgeon and the anesthesiologist.

## 2 Study Objectives

The overall objectives for this study are to establish the efficacy of Hi-VNI in upper airway surgery from the anesthesiologist's and surgeon's perspectives, and to describe the ideal patient and the ideal pathology as well as suitable clinical scenarios when this oxygenation technique should be selected. This study will not change labeling of the Hi-VNI Precision Flow device by the Vapotherm and is not intended to change marketing claims of the manufacturer pertaining to this device.

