## **3 Investigational Plan**

### **3.1 General Design**

This is a prospective, interventional, pilot study that will describe the select cases of upper aerodigestive tract surgery performed at our institution with use of the Hi-VNI device. Data captured will be analyzed with a goal of determining the efficacy of this oxygenation technique for upper airway surgery. We will also collect useful clinical information about the most optimal clinical scenarios for use of this technique based on the cases in our data sample that will demonstrate successful case completion without a need for adjunct oxygenation techniques aside from Hi-VNI such as jet ventilation or endotracheal intubation.

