### Schedule of events:

### 3.4 Study Endpoints

#### 3.4.1 Primary Study Endpoint

The primary endpoint for this study will be case completion rate without alternative mode of oxygenation. In other words, for each case, the ability to complete the surgical procedure with use of only Hi-VNI device for oxygenation will be assessed.

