Using a normal end-tidal CO2 value of 37.5 mmHg and adding this value to the limits of the range of change in TcpCO2 listed above will give us a range of the values for TcpCO2 at the end of the procedure assuming the average duration of the procedure is  $22.5 \pm 4.5$  min. This range of the TcpCO2 at the end of the procedure would be [57.75; 67.88]. Our cutoff of TcpCO2 minus the baseline gradient between TcpCO2 and end-tidal CO2  $> 55$  mmHg is when the mode of oxygenation will be changed from Hi-VNI to an alternate method (endotracheal intubation or HFJV). The baseline gradient will be measured as the TcpCO2 minus the end-tidal CO2 during routine pre-oxygenation with a facemask. Based on the normal distribution assumption, one can deduce that only procedures with the duration one standard deviation away from the mean duration value of 22.5 min will not reach this level of TcpCO2. In other words, approximately 16% of patients will not require alternate means of ventilation (population which falls to the left of the line through a value of (22.5-4.5) on the normal distribution curve or 15.85%). Based on the author's prior experience and operative volume, there are 2-3 elective cases per week performed by the PIs that may qualify based on the inclusion/exclusion criteria to be included in the study. If 3 cases per week is used will equal to 144 qualified cases per year. For the confidence interval of 95% and the margin of error of 5% with the rate of 16%, the calculated sample size will equal to 86 individuals who might have a good chance of having their procedure completed with Hi-VNI without a need to switch to alternate mode of oxygenation. To account for the fact that some patients may not consent to be in the study or may require alternate means of oxygenation after Hi-VNI is used for other reasons, we added 14 patients to the sample size. This would lead to an estimated sample size of 100 individuals.

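### The overview says the study will establish efficacy, but a single-arm pilot with no benchmark for its completion rate can only estimate that rate

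*Combined protocol and SAP*

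**What the plan says.** **Purpose.** Section 2 gives the overall objective as to "establish the efficacy of Hi-VNI in upper airway surgery", seen from the anesthesiologist's and surgeon's perspectives. The Study Summary and section 1 use the same verb. Section 3.1 says the data will be analysed "with a goal of determining the efficacy of this oxygenation technique for upper airway surgery". Section 2.1, the labelled primary objective, is softer: it speaks of evaluating Hi-VNI use, with a focus on SpO2, TcpCO2 and vital signs.

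**Endpoint and design.** The primary endpoint in section 3.4.1 is the "case completion rate without alternative mode of oxygenation". Section 3.2 gives every subject the same intervention. Section 6.1 adds: "No comparison or control group will be used for this study. The calculation of statistical power will not be required".

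**Size.** Section 6.1 expects that "approximately 16% of patients will not require alternate means of ventilation" and sizes the study for the precision of that one proportion, reaching 86 and then 100 subjects.

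**Analysis.** Section 6.2 reports proportions as numbers and percentages. It names t-tests, Mann-Whitney, ANOVA and Kruskal-Wallis at p < 0.05 but no groups to compare. Section 6.3.2 says the primary outcomes will be analysed to obtain averages and standard deviations.

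**The concern.** To say that efficacy has been established, a study needs something to judge its result against: a concurrent comparator, a historical rate, or a minimum acceptable rate fixed beforehand. This plan has none of these for the completion rate. The hypothesis in section 1 concerns ease of airway management, case duration and operating conditions. It does not mention the proportion of cases completed on Hi-VNI alone. The tests in section 6.2 compare groups, and none of them sets one proportion against a reference value.

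The plan therefore promises a verdict that its design cannot return. Section 2 also aims to say when the technique should be selected, and section 12 plans conference presentation and journal publication. A completion rate reported under the heading of established efficacy would reach clinicians without a stated standard behind it.

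**Working it through.** **1. The plan's expected rate (section 6.1).** Inputs: mean duration 22.5 min, SD 4.5 min, normal distribution, cut at 22.5 − 4.5 = 18 min.
P(duration < 18) = Φ((18 − 22.5)/4.5) = Φ(−1) = 15.9%. This agrees with the plan's 15.85%, rounded to 16%.

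**2. The plan's sample size.** Inputs: rate 0.16, margin 0.05, 95% confidence.
- Usual formula: n0 = 1.96² × 0.16 × 0.84 / 0.05² = 206.5, so 207. This is not the plan's figure.
- With a finite population correction for the 144 qualifying cases per year in section 6.1: n = 206.5 / (1 + 205.5/144) = 85.1, rounded up to 86. This matches. The plan does not mention the correction; I infer it because it reproduces the figure.
- 86 + 14 = 100, as stated.

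The calculation concerns precision only. It contains no null rate, no alternative rate and no power.

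**3. What 100 subjects deliver at the expected rate.** With 16 completions of 100, the Clopper-Pearson limits are:
- lower: 2.5th percentile of Beta(16, 85) = 9.4%
- upper: 97.5th percentile of Beta(17, 84) = 24.7%

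The approximate half-width is 1.96 × √(0.16 × 0.84/100) = 7.2 percentage points. The plan's 5 points holds only if one year's 144 cases are treated as the whole population of interest.

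**4. Whether the plan can classify that result.** I looked for a reference value in each section that could hold one:
- Sections 2, 2.1 and 3.1: none.
- Section 3.4.1: the endpoint is defined, with no target.
- Section 6.1: an expected rate used for sizing, not offered as a standard.
- Section 6.2: a significance level, with no null value for the completion rate.
- Section 6.3.2: averages and standard deviations, with no rule.

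**5. How far the verdict depends on the missing value.** The benchmarks below are my assumptions, for illustration only; I propose none of them. The rule is an exact binomial test with one-sided α of at most 0.025 and n = 100.

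| Assumed benchmark | Completions needed | Chance of passing if the true rate is 16% |
|---|---|---|
| 10% | 17 | 0.43 |
| 16% | 24 | 0.025 |
| 50% | 61 | essentially 0 |

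The same true rate gives very different answers according to a number that the plan does not contain.

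**6. The planned summary.** For a 0/1 outcome the mean is the proportion, and the SD is fixed by it: √(0.16 × 0.84) = 0.37 at 16%. The SD adds nothing about precision. The confidence interval on which section 6.1 rests its sample size is not named in section 6.2 or 6.3.2.

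**The case against.** The best defence is that the document is mostly descriptive already. The labelled primary objective in section 2.1 is to evaluate. Section 2.2 is to collect clinical information, and section 3.1 calls the study a pilot that describes selected cases. Section 2 says that labeling will not change. Efficacy is also framed from the clinicians' perspectives, and no section says it will be judged on completion alone. On this view the word efficacy in the overview is loose language.

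Much of this stands. A single-arm study sized for precision is a legitimate pilot, and neither the design nor the sample size needs to change. But section 2.1 does not withdraw the claim made in four other places, and no other endpoint has a success criterion either.

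Three stronger readings are tempting, and the documents support none of them.

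- **That efficacy is untestable because about 84% of cases are expected to fail the primary endpoint.** A low expected rate does not prevent a test; the missing benchmark and comparator do. The 84% is also insecure. It is the complement of 16% and covers CO2-driven switches only, while section 6.1 allows for switches for other reasons. On the plan's own inputs the 55 mmHg threshold is reached at (55 − 37.5)/1.125 = 15.6 min. Φ((15.6 − 22.5)/4.5) is about 6%, so about 94% would switch. Section 3.3 expects most cases to finish within 20 minutes, whereas 22.5 ± 4.5 min implies Φ((20 − 22.5)/4.5) = 29%. Those passages need to be reconciled, but that is a separate matter.
- **That the favourable conclusion is settled in advance.** No section says efficacy will be declared whatever the result, and section 1 undertakes to document disadvantages as well as advantages.
- **That a pass mark must be added, or conclusions confined to the completion rate.** The mismatch can be removed without a pass mark, and adding one could mean redesign, as the table shows. Confining conclusions to completion would discard the physiologic objective in section 2.1 and the secondary endpoints in section 3.4.2.

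**Conclusion.** The point holds as a mismatch between claim and design. Four overview statements promise that efficacy will be established or determined. The design yields one estimated proportion with nothing to judge it against, and section 6.3.2 summarises that proportion unsuitably. At the plan's expected 16%, the result would be 16 of 100 with an exact 95% interval of 9.4% to 24.7%, which the plan cannot call efficacious or otherwise.

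The interval assumes that all 100 subjects are analysed and that the observed rate equals the expected one. The main conclusion depends on neither assumption, because no reference value is given for any rate. The pilot itself remains sound as a descriptive study. The matter should be corrected because it limits what may be concluded from the results.

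**What to change.** 1. In the Study Summary and sections 1, 2 and 3.1, replace the wording about establishing or determining efficacy with wording in line with section 2.1, for example: evaluate Hi-VNI use and estimate the proportion of cases completed on Hi-VNI alone.
2. In section 6.3.2, state that the primary endpoint will be reported as a proportion with its exact (Clopper-Pearson) 95% confidence interval instead of a mean and standard deviation, and that no claim of established efficacy will be drawn from it.
3. Keep the physiologic objective in section 2.1 and the secondary endpoints in section 3.4.2, and label them descriptive.

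**Cost.** Edits to the text and one standard interval calculation, with no added subjects, data or procedures. The downside is a more modest claim, which is appropriate for a pilot.
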